8.3 Handling of the Difference between the Scheduled and the Actual Sampling Times

The actual clock time for dosing and each collection time for the PK samples will be recorded. For all sampling times, the actual sampling times relative to dosing will be calculated as the difference between the actual clock time of sampling and the actual clock time of dosing. The actual post-dose sampling times relative to dosing expressed in hours and rounded off to three decimal digits will be used to calculate the PK parameters, except for pre-dose samples occurring prior to dosing, which will always be reported as zero (0.000), regardless of the time difference. Scheduled sampling times will be presented in concentration tables and mean graphs, while actual sampling times will be presented in the individual graphs.

8.4 Plasma PK Endpoints

[REDACTED]
[REDACTED]

STATISTICAL ANALYSIS PLAN
BBT176-ONC-001

[REDACTED]

[REDACTED]

[REDACTED]
[REDACTED]
[REDACTED]
[REDACTED]

[figure not shown]
[REDACTED]

[figure not shown]
Additional PK parameters may be computed if deemed appropriate.

8.5 Statistical Analyses

[REDACTED]
[REDACTED]
[REDACTED]
[REDACTED]
[REDACTED]

STATISTICAL ANALYSIS PLAN
BBT176-ONC-001

9. PHARMACODYNAMIC (PD) ANALYSES

No formal statistical analysis of pharmacodynamics endpoints will be performed. Data listings will be created for each pharmacodynamics biomarker by cohort and patient.

Summary tables of values (number of observations, mean, median, standard error of the mean, standard deviation) will be created for each pharmacodynamics biomarker.

10. SAFETY ANALYSES

All safety analyses will be based on the Safety population. Safety variables to be assessed will include AEs, laboratory test results (hematology, clinical chemistry, and urinalysis), ECGs, weight, vital signs.

10.1 Extent of Exposure

Study drug exposure will be summarized for each dose escalation cohort and all patients in the dose escalation phase. Duration of treatment is defined as the last dose date minus the first dose date plus 1. Drug adjustments and interruptions are listed and summarized for each cohort.

10.2 Adverse Events (AEs)

An AE is any untoward, undesired, or unplanned event in the form of signs, symptoms, disease, or laboratory or physiologic observations occurring in a person given a test article (study drug) in a clinical study. The description found in the revised NCI CTCAE version 5.0 will be utilized for AE reporting.

All AEs will have their relationship to study treatment assessed as follows:

- Definite – The AE is *clearly related* to the study treatment
- Probable – The AE is *likely related* to the study treatment
- Possible – The AE *may be related* to the study treatment
- Unlikely – The AE is *doubtfully related* to the study treatment
- Unrelated – The AE is *clearly NOT related* to the study treatment

A serious AE (SAE) is an AE that:

- Results in death.
- Is life-threatening.
- Requires inpatient hospitalization or prolongation of an existing hospitalization.
- Results in a persistent or significant disability or incapacity.
- Results in a congenital anomaly or birth defect.
- Additionally, important medical events that may not result in death, be life-threatening, or require hospitalization may be considered SAEs when, based on appropriate medical judgment, they may jeopardize the patient and may require medical or surgical intervention to prevent one of the outcomes listed in this definition.

A Treatment-emergent AE (TEAE) is an AE with an onset day on or after the day of the initial dose of study drug.

AEs of special interest (AESI) is an AE that:

- Gastrointestinal, skin (>Grade 2), pulmonary (\geq Grade 2), and/or serious events requiring reporting to the Sponsor as an SAE.
- Any laboratory hepatic toxicity meeting Hy's law criteria for suspected severe drug induced liver injury, defined as a rise in serum aminotransferase (AST or ALT) of $>3\times$ ULN and total bilirubin $\geq 2 \times$ ULN, in the absence of any alternative reason (e.g., liver metastasis, liver disease, or concomitant medication)

AE terms recorded on the eCRF will be mapped to preferred terms using [REDACTED]

[REDACTED] An overall summary will be provided of the number and percentage of patients reporting AEs, TEAEs, treatment-related TEAEs, serious TEAEs, treatment-related serious TEAEs, AEs of special interest (AESIs), TEAEs leading to study drug withdrawal and TEAEs leading to death. In the overall summary, additionally, the number and percentage of patients with at least one severe TEAE, with at least one moderate TEAE but no severe TEAE and with only mild TEAEs will be provided.

The number and percentage of patients with AEs will be summarized for each dose level and overall in Part 1, and by cohort and overall in Part 2 according to the system organ class and preferred term. AEs (including AESI) will be summarized for overall frequency (number and percentage of patients), worst reported severity, and relationship to study treatment for each preferred term per patient. SAEs will be similarly summarized. Listings of death, SAEs, and AEs leading to early termination of study treatment or premature withdrawal from study will be also provided.

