**Statistical Methods:**

**Number of Patients**

*Part 1* – [REDACTED]

Part 1 of the study will include approximately up to [REDACTED] with locally advanced or metastatic NSCLC with EGFR mutation. Additional patients may be required, depending on the number of cohorts and the number of evaluable patients needed.

*Part 2* – [REDACTED]

An enrichment phase [REDACTED] selected mutant types will be enrolled and dosed at the RP2D. Given no clinical efficacy had been studied and reported in this patient group, there will be no statistical hypothesis assumed in regard to efficacy. Descriptive statistics will be applied to summarize efficacy.

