### 3.3 Schedule of Activities (SoA)

#### Part 1 (Dose-Escalation and RP2D Exploratory Cohorts, Phase 1)

		Treatment Phase	EOT a	Safety F/U b
--	--	-----------------	------------------	-------------------------

Screening Phase	Cycle 1	[REDACTED]	[REDACTED]	[REDACTED]	[REDACTED]

[figure not shown]
- a. End of Treatment (EOT) visit: the last day of study treatment administration.
- b. Safety F/U visit: 30 days ( $\pm$  3 days) after the last dose of study treatment or prior to initiation of another systemic anti-cancer therapy, whichever occurs first.
- c. The first dose of each cycle is considered Day 1 of each cycle, and cycles will repeat every 21 days unless there is a treatment delay.
- d. On Cycle 1, Day 1 before taking dose: confirmation of inclusion/exclusion criteria.
- e. Complete physical exams, to include auscultation of the heart for new development of murmur, at Screening, Day 1 of each Cycle, EOT, and Safety F/U visit. If physical or lab findings suggest cardiac damage, echocardiogram or MUGA should be done.

[figure not shown]

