### 6.3 Treatment Duration and End of Study Definition

#### 6.3.1 Treatment Duration

Patients should continue on treatment with BBT-176 until RECIST v1.1 defined progression, unacceptable toxicities, symptomatic progression or until the criteria for treatment discontinuation criteria ([Section 9](#)) are met.

A patient is considered to have completed the study when all phases of the study, including the last visit or the last scheduled procedure shown in the Schedule of Activities (SoA; [Section 3.3](#)), have been completed.

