## Safety Follow-up

This document is confidential.

Safety follow-up should be performed [REDACTED] after the last administration of study drug or immediately before initiation of any other cancer therapies.

- Complete physical examination, including measurement of weight, auscultation of the heart for new development of murmur (if physical or lab findings suggest cardiac damage, echocardiogram or MUGA should be done)
- ECOG performance status
- Vital signs
- Laboratory tests
- Serum pregnancy test in female patients of childbearing potential
- 12-lead ECG
- Concomitant medications
- AE assessments

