#### 10.6.4 Time Period and Frequency for Event Assessment and Follow-up

Assessments for AEs will be conducted on all study visits indicated in the SoA ([Section 3.3](#)). The PI will record all reportable events with start dates occurring any time after informed consent is obtained until 30 days (for non-serious AEs) after the last day of study participation or until resolution or stabilization (for SAEs). At each study visit, the Investigator will inquire about the occurrence of AE/ SAEs since the last visit.

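### The SAP's treatment-emergent period has no end, so any event recorded after the next anticancer therapy starts counts in the all-cause TEAE lines

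*SAP*

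**What the plan says.** **Definition.** SAP 10.2 states: "A Treatment-emergent AE (TEAE) is an AE with an onset day on or after the day of the initial dose of study drug". The sentence is complete and not blacked out. It has a start and no end.

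**Recording.** Protocol 10.6.4 has the investigator record events that start after consent "until 30 days (for non-serious AEs) after the last day of study participation or until resolution or stabilization (for SAEs". The protocol does not define the last day of participation, and the clause does not mention new anticancer therapy. The same section says "Assessments for AEs will be conducted on all study visits indicated in the SoA".

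**Last visit.** Footnote b of the Part 1 Schedule of Activities (Protocol 3.3) puts the Safety F/U visit 30 days, give or take 3, "after the last dose of study treatment or prior to initiation of another systemic anti-cancer therapy, whichever occurs first". The Safety Follow-up text in Protocol 10.5, which appears once for each part, places the visit "after the last administration of study drug or immediately before initiation of any other cancer therapies". The number of days there is wholly or partly blacked out. On completion, Protocol 6.3.1 says "A patient is considered to have completed the study when all phases of the study", up to the final visit or procedure in the schedule, are done.

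**Use.** The overall summary in SAP 10.2 counts patients with AEs and TEAEs, then "treatment-related TEAEs, serious TEAEs, treatment-related serious TEAEs, AEs of special interest (AESIs), TEAEs leading to study drug withdrawal and TEAEs leading to death". It adds three lines for patients whose worst TEAE is severe, moderate or mild.

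**The concern.** A treatment-emergent period is meant to hold the events that could plausibly belong to exposure to the study drug. When it has no end, the data-collection rule sets the end by default. Here that rule is tied to participation rather than to the last dose, and it runs on through a change of therapy.

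Patients are treated until progression or intolerance, so a further anticancer therapy soon after the last dose is foreseeable. The Safety F/U rule itself provides for one. Toxicity of that next therapy, once recorded, would be reported as emergent on BBT-176. The lines at stake are those that take no account of causality: any TEAE, serious TEAE, the severity lines and TEAE leading to death. The trial has no control arm against which such events would cancel out.

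The SAP already uses the start of further anticancer treatment as a cut-off for best overall response (SAP 7.2). It has no matching cut-off for safety.

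**Working it through.** The plan gives no figure on this point, so there is none to reproduce. The check sets the rules side by side and counts days. Let day 0 be the last dose and let d be the day the next anticancer therapy starts. The value of d is an assumption, since the documents give none.

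**Inputs**
- TEAE period: first dose onward, no end (SAP 10.2).
- Non-serious recording: to 30 days after the end of participation (Protocol 10.6.4).
- SAE recording: no limit on onset is stated. Resolution or stabilization describes how long an event is followed, not the latest day it may begin.
- Safety F/U: day 30 ± 3, so day 27 to 33, or before new therapy if that comes first (Protocol 3.3, footnote b).

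**Reading A: participation ends at Safety F/U** (the reading that Protocol 6.3.1 suggests)
- No early new therapy: recording ends between 27 + 30 = day 57 and 33 + 30 = day 63.
- New therapy on day d, straight after an early Safety F/U visit: recording ends at about day d + 30. Time on the new therapy is (d + 30) − d = about 30 days, whatever d is.

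**Reading B: participation ends at the last dose**
- Recording ends on day 30. Time on the new therapy is 30 − d days. With d = 10 assumed, that is 30 − 10 = 20 days.

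**SAEs, either reading:** no limit to the overlap is stated.

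| | Reading A | Reading B |
|---|---|---|
| Non-serious recording ends, no early switch | day 57 to 63 | day 30 |
| Non-serious recording on next therapy, switch on day d | about 30 days | 30 − d days |
| SAE onset limit | none stated | none stated |

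Under both readings, every event recorded in the overlap meets the TEAE definition.

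**Which lines move.** The overall summary counts patients, so a late event moves a line only if the patient is not already in it. The line for TEAEs leading to drug withdrawal cannot move, because the drug has already stopped. The system organ class and preferred term tables are specified for AEs, not TEAEs, so they do not depend on this definition. That leaves the all-cause, serious, severity and fatal TEAE lines.

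**Weight of one patient.** Protocol 12.8 mentions review at twelve patients per subgroup and up to 30 per RP2D exploratory cohort. One patient wrongly placed in a line shifts it by 1/12 = 8.3 percentage points or 1/30 = 3.3 points. This shows scale only and does not estimate how many patients are affected.

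**After the fix.** If the period ends at the earlier of day 30 or the day before new therapy, the overlap is 0 days, for serious and non-serious events alike. Only later events judged related to BBT-176 remain.

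**The case against.** The strongest reply is that few such events will be recorded. AEs are assessed at scheduled visits, the last visit described is Safety F/U, and it comes before any new therapy. Protocol 10.6.5 speaks of events occurring on study. Beyond Safety F/U, collection rests on one clause of 10.6.4 with no visible visit behind it. This stands as a limit on size. It does not remove the point, because 10.6.4 still requires recording and 10.6.6 requires any SAE to be reported once the site is aware of it.

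A second reply is that treatment-related TEAEs and treatment-related serious TEAEs have their own lines, based on a five-level causality scale. That partly protects those lines. The all-cause lines have no such protection.

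Three stronger readings are tempting, and the documents support none of them.
- A reader might infer that collection runs to about 60 days after dosing and that a fixed share of the TEAE period lies on the next therapy. The 57 to 63 days hold only under Reading A without an early switch. They then measure time beyond a 30-day window, not time on new therapy, and a share of calendar time says nothing about event counts.
- A reader might infer that the Part 1 primary endpoint is contaminated. Protocol 5.3.1.1 words it as AEs and laboratory abnormalities defined as DLTs, and DLTs are evaluated over the first 21 days (Protocol 7.5 and 10.2.2).
- A reader might infer that the RP2D is distorted. Protocol 12.8 bases that recommendation on safety, PK and efficacy including biomarker data, as reviewed by the SMC. No passage says that TEAE tables set it.

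**Conclusion.** The point holds as a gap in a reporting definition. Followed as written, SAP 10.2 and Protocol 10.6.4 together count events recorded on the next anticancer therapy as emergent on BBT-176, under either reading of when participation ends. The overlap in the non-serious window is about 30 days (Reading A) or 30 − d days (Reading B), and for SAEs no limit is stated. The number of events cannot be derived from the documents and may be small. The effect is confined to the all-cause, serious, severity and fatal TEAE lines of the overall summary.

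This rests on the visible text. The Schedule of Activities grids, part of the Part 1 procedures and the partial-date appendix of the SAP cannot be read. A gap in SAP 10.2 just before the overall summary continues the coding-dictionary sentence, so it is unlikely to hold an end date. A later AE contact in an unseen grid would make capture larger, not smaller.

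This is a cheap improvement to make before the tables are run. It does not threaten the trial's main conclusions.

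**What to change.** **SAP 10.2.** Define a TEAE as an AE with onset or worsening from the first dose to the earlier of 30 days after the last dose or the day before new systemic anticancer therapy, plus any later event judged related to BBT-176. List the other later events separately. The 30 days are borrowed from the Safety F/U timing, since the documents state no TEAE end. Say which of the five causality categories count as related for this purpose, and how a later event with missing causality is handled.

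**Protocol.** Leave AE collection as it is. Define the last day of study participation, and reconcile 10.6.4 with the Safety F/U timing in footnote b of the Schedule of Activities and in the Safety Follow-up text of 10.5.

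**Cost.** A sentence or two in the SAP and a clarification at the next protocol amendment. No collected data are lost. The start date of further anticancer therapy is already needed for best overall response under SAP 7.2. The downside is that late events judged unrelated move from the TEAE summary to listings. Keeping later related events in the definition means that delayed BBT-176 toxicity, serious or not, stays in the summary even after an early switch.

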#### 6.2 Justification for Dose

BBT-176 [REDACTED] will be the starting dose tested in Part 1 (dose-escalation study).

- Acute gastrointestinal toxicities like nausea, vomiting and diarrhea may be less with BID dosing schedule.

- [REDACTED]
- [REDACTED]
- [REDACTED]
- [REDACTED]

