**10.6.8      Adverse Events of Special Interest**

DLT evaluation will occur in Part 1. Please refer to [Section 10.2.2](#) for definition of DLTs.

AEs of special interest (AESI) for the purposes of this study, based on the known safety profiles of EGFR inhibitors, include gastrointestinal (>Grade 2), skin (>Grade 2), pulmonary ( $\geq$ Grade 2), and/or serious events requiring reporting to the Sponsor as an SAE.

Any laboratory hepatic toxicity meeting Hy's law criteria for suspected severe drug induced liver injury, defined as a rise in serum aminotransferases (AST or ALT) of  $>3 \times$  ULN and total bilirubin  $\geq 2 \times$  ULN, in the absence of any alternative reason (e.g., liver metastasis, liver disease, or concomitant medication), will also be considered an AESI.

Protocol-specified AESI are to be reported in an expedited manner, similar to an SAE, even if they are not an SAE (within 24 hours).

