1. INTRODUCTION

This document outlines the statistical methods to be implemented during the analyses of data collected within the scope of Bridge Biotherapeutics Protocol Number BBT176-ONC-001 entitled “A Phase 1 / 2, Open-Label Study to Assess the Safety, Tolerability, Pharmacokinetics, and Anti-tumor Activity of BBT-176 in Patients with Advanced Non-Small Cell Lung Cancer (NSCLC) who Progressed Following Prior Therapy with an Epidermal Growth Factor Receptor Tyrosine Kinase Inhibitor (EGFR TKI) Agent.” The statistical methods described herein are based on the analyses proposed in the Protocol version [REDACTED]. This study is designed in 2 parts designated Part 1 (dose-escalation study) and Part 2 [REDACTED].

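### SAP 10.2 attaches no grade limit to gastrointestinal AESIs while Protocol 10.6.8 limits them to above Grade 2, so the AESI counts could take in low-grade events

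*SAP*

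**What the plan says.** Protocol 10.6.8 lists the organ classes that make up the AESIs, each with its own limit: "gastrointestinal (>Grade 2), skin (>Grade 2), pulmonary", the pulmonary class being set at Grade 2 or higher. It adds serious events and laboratory cases that meet Hy's law. The definition also has an operational use: "Protocol-specified AESI are to be reported in an expedited manner, similar to an SAE", within 24 hours and whether or not the event is serious.

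SAP 10.2 gives the same list in the same order, with the same pulmonary limit, serious-event clause and Hy's law criteria. Its opening words are "Gastrointestinal, skin (>Grade 2), pulmonary", so the gastrointestinal term carries no limit of its own.

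SAP 10.2 then uses the category twice. The overall summary gives the number and percentage of patients in a run of categories that includes "AEs of special interest (AESIs), TEAEs leading to study drug withdrawal and TEAEs leading to death". Further tables follow: "AEs (including AESI) will be summarized for overall frequency (number and percentage of patients), worst reported severity, and relationship to study treatment", by preferred term.

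**The concern.** An SAP definition is the specification from which a derived flag is programmed. If the flag follows the SAP bullet as written, any gastrointestinal event of any grade qualifies. The class is likely to be well populated: Protocol 6.2 says "Acute gastrointestinal toxicities like nausea, vomiting and diarrhea may be less with BID dosing schedule", and Protocol 4.2 attributes part of the toxicity of the first-generation EGFR inhibitors to inhibition of wild-type EGFR in skin and intestine.

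Two things are at stake. The AESI percentage in the study report could mix minor gastrointestinal complaints with the events the protocol singled out. It could also fail to reconcile with the AESIs that sites sent in under the 24-hour rule, which follows the protocol's narrower definition.

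**Working it through.** The plan gives no figure to reproduce here, and the point depends on no sample size, error rate or event count. The check is a comparison of the two definitions followed by a trace of where the SAP uses its own.

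**Step 1. The definitions side by side** (CTCAE version 5.0 grades in both documents).

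| Component | Protocol 10.6.8 | SAP 10.2 |
|---|---|---|
| Gastrointestinal | above Grade 2 | no grade attached |
| Skin | above Grade 2 | above Grade 2 |
| Pulmonary | Grade 2 or higher | Grade 2 or higher |
| Serious events reportable as SAEs | included | included |
| Hy's law | AST or ALT >3 × ULN and total bilirubin ≥2 × ULN, no alternative reason | same |

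Only the gastrointestinal row differs.

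**Step 2. What the difference adds.** Under the protocol, gastrointestinal events qualify at Grades 3 to 5. Under the SAP read literally, they qualify at Grades 1 to 5. The difference is Grades 1 and 2. Serious gastrointestinal events of those grades already qualify in both documents through the serious-event clause, so what the literal SAP reading adds is the non-serious Grade 1 and 2 gastrointestinal events.

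**Step 3. Whether other SAP text closes the gap.** The bullet is unbroken, with no redaction mark or gap inside it; the nearest redaction comes later, where the coding dictionary would be named. No visible SAP passage restores the limit, refers to Protocol 10.6.8 for AESIs, or says that the protocol definition prevails.

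**Step 4. What can be said about size.** Let *p* be the proportion of patients with at least one AESI under the protocol definition. Let *q* be the proportion with none, but with at least one non-serious Grade 1 or 2 gastrointestinal event. Then:

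- protocol AESI row = *p*
- literal SAP AESI row = *p* + *q*, with 0 ≤ *q* ≤ 1 − *p*

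The SAP set contains the protocol set, so the row can rise or stay the same but cannot fall. Neither *p* nor *q* can be obtained from the documents, so only the direction is established.

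**Step 5. What is not affected.** The Part 1 primary endpoint is adverse events and laboratory abnormalities defined as DLTs (Protocol 5.3.1.1). The Part 2 primary endpoint is ORR (Protocol 5.3.2.1). Neither uses the AESI category, and no visible escalation or monitoring-committee rule uses the SAP's AESI count.

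**The case against.** The best case for the SAP has four parts.

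- **The bullet can be read another way.** The limit after skin could cover both terms before it. Gastrointestinal and skin share the same limit in the protocol, so that reading reproduces the protocol exactly. This stands as a possibility, and it is why the SAP could, rather than will, count all grades. It does not clear the SAP: the protocol writes the limit out for each class, and a bullet that supports two derivations is not an adequate specification.
- **The flag may not be derived from the SAP at all.** Neither document says whether AESI status is programmed from organ class and grade or taken from an investigator's entry. With an investigator flag based on the protocol, the counts would follow the protocol. This also stands, and the visible text does not settle it.
- **The SAP may follow an earlier protocol.** It says "The statistical methods described herein are based on the analyses proposed in the Protocol version", and the version number is redacted. Its date line reads 28 JAN 2021, whereas the supplied protocol's reference list contains an item dated May 2021. The SAP's Part 1 objectives (2.1.1 and 2.1.2) include combination with cetuximab, which Protocol 5.1 does not. A reader might infer that the SAP removed a limit it had been given. The documents do not show that: the protocol may have added the limit later, and its amendment history is not readable. Either way, the two documents as supplied disagree.
- **Severe events are not lost.** A reader might infer that low-grade events would hide the severe ones. SAP 10.2 tabulates worst severity by preferred term, counts patients with severe, moderate and mild treatment-emergent events separately, and summarizes and lists serious events. Severe gastrointestinal events stay visible under either reading.

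**Conclusion.** The inconsistency is real, and it is confined to one descriptive safety category. The protocol sets a gastrointestinal limit; the SAP as written does not. If the bullet is read literally and the flag is programmed from it, the AESI row of the overall summary and the AESI totals could be inflated by patients whose only qualifying event is a non-serious Grade 1 or 2 gastrointestinal event, and would then disagree with site-reported AESIs. Both conditions are assumptions that the documents neither confirm nor exclude.

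No size can be attached. Any percentage for the inflation would rest on assumed gastrointestinal rates and should not be used to rank the point. Nor should a reader infer that safety reporting from sites is compromised: expedited reporting follows Protocol 10.6.8, which is clear.

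**What to change.** Before the AESI outputs are programmed, reconcile the bullet in SAP 10.2 with Protocol 10.6.8. Either state the protocol's gastrointestinal limit (above Grade 2) directly after the gastrointestinal term, or replace the list with a citation of Protocol 10.6.8 as the governing AESI definition. This sets no new threshold; it brings the SAP into line with the protocol's own. It would also help to say in the same place whether AESI status is derived from coded term and grade or taken from the investigator's report, and to confirm which protocol version the SAP follows.

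The cost is one line in the SAP, or two with the derivation source. No data collection, sample size or endpoint changes.

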##### **5.3.1.1 Primary Endpoint**

- Safety and tolerability (incidence of adverse events [AEs] and clinical laboratory abnormalities defined as DLTs)

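### The detailed AE tables count events from informed consent rather than first dose, and the TEAE definition does not cover pre-dose events that worsen on BBT-176

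*SAP*

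**What the plan says.** Protocol 10.6.4 sets the start of AE collection: "The PI will record all reportable events with start dates occurring any time after informed consent is obtained".

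SAP 10.2 defines the treatment-emergent subset by onset day: "A Treatment-emergent AE (TEAE) is an AE with an onset day on or after the day of the initial dose of study drug". There is no clause for an event already present that worsens after dosing.

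The same section then specifies two layers of output:

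- An overall summary of patients "reporting AEs, TEAEs, treatment-related TEAEs, serious TEAEs" and further categories, with severe, moderate and mild counts on TEAEs. AESIs appear in it without a treatment-emergent restriction.
- The detailed tables. By organ class and preferred term: "The number and percentage of patients with AEs will be summarized for each dose level and overall in Part 1", with a parallel rule by cohort for Part 2. Then: "AEs (including AESI) will be summarized for overall frequency (number and percentage of patients), worst reported severity, and relationship to study treatment". SAEs are handled in the same way.

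Protocol 11.7 and the safety paragraph of the synopsis also describe these tables in terms of AEs, so the SAP follows the protocol here.

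**The concern.** A table of AEs by dose level is read as a description of what happened on that dose. If its input includes events between consent and first dose, incidence and worst grade at a dose level can include events that the drug could not have caused. A screening event that resolved before any BBT-176 could even supply the worst grade shown for a preferred term.

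This boundary matters more than usual here. Protocol 7.2 excludes an EGFR TKI only within 8 days of the first dose, and Protocol 4.3.1 expects the risks of BBT-176 to resemble those of other EGFR TKIs. Pre-dose events may therefore fall under the same preferred terms as drug effects.

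The TEAE definition errs in the other direction. Protocol 7.2 admits patients with Grade 1 residual toxicity, so low-grade events that later worsen are plausible. Under an onset-only rule, an event first seen in screening stays outside the TEAE counts even if its grade rises on drug.

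What is at stake is the reported safety profile by dose level and cohort, including the Part 2 secondary endpoint of AE incidence (Protocol 5.3.2.2).

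**Working it through.** The plan states no figure on this point, so there is none to reproduce. The check is a comparison of the texts, followed by an illustration of scale.

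**1. Does AE in the SAP already mean after first dose?** The SAP definition speaks of an event "occurring in a person given a test article (study drug) in a clinical study". That limits the person, not the time. The overall summary lists AEs and TEAEs as separate lines, which would be redundant if every AE were post-dose. With collection starting at consent, a programmer following the text would put screening events of dosed patients into the detailed tables.

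**2. Is on-drug worsening captured elsewhere?** Protocol 10.6.5 sends conditions highly likely to pre-date consent to medical history and records their deterioration as an AE. That rule follows a sentence about pre-consent conditions. It does not clearly say that an AE starting after consent and before dosing gets a new record or onset date when it worsens. If it keeps its original onset, it is not a TEAE.

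**3. Do the two gaps interact?** At present the all-AE worst-severity table would still show the worsened grade. If the detailed tables move to TEAEs and the definition stays as it is, that event drops out of them too. The two changes belong together.

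**4. Are dose decisions touched?** Protocol 10.2.2 runs the DLT window to the last day of Cycle 1, counted from the start of dosing. Pre-dose events cannot enter DLT counts.

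**5. Scale by group size.** One patient with only pre-dose events moves a percentage by 100/n. The chance of at least one patient with a pre-dose AE is 1 − (1 − q)^n, where q is an assumed share of patients; the documents give none. Groups of 6 and 12 are the SMC review points in Protocol 12.8; n = 3 is assumed, because the escalation cohort size is redacted.

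| n | Shift per patient | q = 5% | q = 10% | q = 20% |
|---|---|---|---|---|
| 3 | 33.3 points | 14.3% | 27.1% | 48.8% |
| 6 | 16.7 points | 26.5% | 46.9% | 73.8% |
| 12 | 8.3 points | 46.0% | 71.8% | 93.1% |

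For example, with n = 6 and q = 10%: 1 − 0.9^6 = 46.9%.

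**6. Scale by time at risk.** Assume a constant event rate, screening S of 14 to 28 days (actual length redacted) and treatment of 42 to 84 days. Adding the 30-day follow-up gives T = 72 to 114 days. Let p be the true on-treatment incidence and f the background share of the on-treatment rate. Reported incidence = 1 − (1 − p)^(1 + f·S/T).

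- f = 1, p = 20%: 1 − 0.8^(128/114) = 22% up to 1 − 0.8^(100/72) = 27%. For p = 30% the range is 33% to 39%.
- f = 0.5, p = 20%: 1 − 0.8^(1 + 0.5·14/114) = 21% up to 1 − 0.8^(1 + 0.5·28/72) = 23%.
- f = 0: 20%, no inflation.

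**The case against.** The strongest reply is that the consequences are limited and partly covered already.

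- A reader might infer that screening events distort dose escalation or the choice of RP2D. The documents do not support that. DLTs are counted from the start of dosing. Under Protocol 12.8 the SMC receives SAEs, potential DLTs and PK results as they arise, and it uses the model and safety findings for the next dose and the MTD. No passage says that these SAP tables drive the RP2D.
- A reader might also infer that the Part 1 primary endpoint is inflated. Protocol 5.3.1.1 reads "Safety and tolerability (incidence of adverse events [AEs] and clinical laboratory abnormalities defined as DLTs". If the closing words govern both nouns, only DLT-defined events count and pre-dose events cannot enter. The wording does not settle this, so the claim cannot be made. The Part 2 secondary endpoint in Protocol 5.3.2.2 has no such qualifier.
- The overall summary already gives TEAE counts by severity, relatedness and seriousness, and a relationship table can show a screening event as unrelated. That stands. What is missing is treatment-emergent detail by organ class and preferred term.
- Protocol 10.6.5 diverts pre-consent conditions to medical history, which reduces the number of screening AEs, and its deterioration sentence could be read more widely. This narrows the worsening gap without clearly closing it.
- Text is blacked out just before the overall summary in SAP 10.2, and in Protocol 10.2.3 and 11.4. The SAP gap probably holds the dictionary version, since Protocol 11.7 names MedDRA at the matching place. A restriction to TEAEs in the hidden text is unlikely but cannot be excluded.

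**Conclusion.** Both parts hold on the visible text. As written, the detailed AE tables attribute events between consent and first dose to a dose level or cohort, and the TEAE counts can miss an event that starts in that interval and worsens on drug. The effect is on reported safety tables in both parts, including the Part 2 secondary endpoint. It does not reach DLT or MTD decisions.

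The size is unknown. The firmest statement is arithmetical: one patient with only pre-dose events moves a rate by 16.7 points in a group of six. A reader might take the shift from 20% to 22–27% as the expected bias. It is the upper bound of the illustration, holding only if all on-treatment events are background, and it rests on assumed screening and treatment lengths and a constant rate. For purely drug-caused events the inflation is zero.

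The change should be made, because the wording is specific, the result is avoidable, and the groups are small.

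**What to change.** In SAP 10.2:

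- Base the tables by organ class and preferred term, worst severity, relationship, AESI and SAE on TEAEs, and apply the same restriction to the AESI line of the overall summary.
- Put AEs that precede first dose in a separate listing.
- Define a TEAE as an AE with onset on or after first dose, or one present before first dose whose CTCAE grade increases on or after it.
- State that such worsening is recorded with its own date.

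Align Protocol 11.7 and the safety paragraph of the synopsis; a SAP edit alone would leave the two documents describing different tables.

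The cost is SAP and protocol wording, a change of input flag in the table programs, and possibly an eCRF completion instruction on dating a grade increase.
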